It will be a prospective, randomized cross over study in which participants will act as their own control. Ambient air pollution will be recorded in Dalkhola town in each ward/unit. Based on the recordings, the top 5 wards/units will be selected. Participants who live within 300m radius of the monitoring area of each ward/unit will be screened for hypertension and diabetes by community health workers (CHWs) who are trained to record blood pressure and blood glucose level by the investigators. After screening and obtaining informed consent, they will be randomized to either intervention arm or control arm. Both arms will be for 4 weeks duration and the blood pressure and blood glucose levels will be recorded on Day 0, end of week 2 and end of week 4. Intervention group participants will be given an indoor air purifier (to be used daily for 12 hours between 8 PM and 8 AM) and a washable N95 mask (to be used when the participant is outdoors). The control arm participant will receive an identical air purifier, but without the filter. Similarly, the control arm participant will continue to wear the N-95 mask during the control phase, with the N-95 filter removed by the health worker. This will ensure blinding of the participant. All blood pressure and blood glucose measurements will be made by a health worker who is blinded to the study group of the participant. At the end of the first 4 weeks, there will be a washout period of 2 weeks in which the participants will return to their usual state. The participants who were initially in the intervention arm will be placed in the control arm and vice versa. 15% of the participants will be randomly selected for indoor air

pollution monitoring during each arm. We will have a run-in period for 2 day for the intervention – using air purifier and wearing N95 mask. Participants who show good adherence will be recruited in the study.

Inclusion Criteria:

Hypertension arm

- 1. Individuals age 18-70 years old with systolic blood pressure between 130-160 mmHg, regardless of medication use
- 2. Stable hypertension for the past 3 months with no medication changes
- 3. No planned medication changes for the duration of the study
- 4. Exposure to outdoor air pollution above a certain threshold (pollution levels will be measured using AirVeda devices)
- 5. Individuals who sleep in a closed space (such as a bedroom) for minimum of 6 hours/daily.
- 6. Use of gas (LPG)/electricity for cooking purposes

Diabetes arm

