- 1. Individuals age 18-70 years old with fasting blood glucose between 126-180 mg/dL, regardless of medication use
- 2. Stable diabetes for the past 3 months with no medication changes
- 3. No planned medication changes for the duration of the study
- 4. Exposure to outdoor air pollution above a certain threshold (pollution levels will be measured using AirVeda devices)
- 5. Individuals who sleep in a closed space (such as a bedroom) for minimum of 6 hours/daily.
- 6. Use of gas (LPG)/electricity for cooking purposes

Exclusion Criteria

- 1. Unwilling to participate
- 2. Unstable blood pressure and/or blood glucose level requiring frequent medication changes
- 3. Individual suffering from a physical or mental illness that precludes active study participation
- 4. Current smoker
- 5. Planned vacation/absence from the study site
- 6. Patients with life expectancy < 12 months
- 7. Pregnant patients

Screening, recruitment and randomization:

Participants from the selected ward will be screened by the community health worker for hypertension and diabetes. For those who are diagnosed with HTN/DM, she will record the BP/BG level during the first home screening visit. The screening will be based on form 0 which has been attached with the protocol in the appendix. Participants who were never diagnosed with HTN/DM but had elevated BP/BG level during the first visit will not be included in the study. At the time of recruitment, CHWs will fill out form 1 of the screening questionnaire, which has also been attached. She will also obtain informed consent, which will be explained and printed in the local language. Participants will be randomized using sealed, opaque envelopes.

Sample size and power calculation:

128 participants (calculated with 80% power; alpha level of 0.05; to detect the difference of 2mmHg; assumed SD 8) with hypertension will be randomly exposed to one of two arms for 4 weeks, followed by exposure to the other arm.

Similarly, 33 participants (calculated with 80% power; alpha level of 0.05; to detect the difference of 10mg/dL; estimated SD 20) with diabetes will be randomly exposed to one of two arms for 4 weeks, followed by exposure to the other arm.

	2 mmHg	3 mmHg	4 mmHg
SD=6	73	33	20
SD=7	98	45	26
SD=8	128 paired observations	58	33

	10 mg/dL	15 g/dL	20 mg/dL
SD=15	20	10	7
SD=17	25	12	8
SD=20	33 paired observations	16	10

Intervention group:

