Intervention arm will be for 4 weeks. Blood pressure and/or blood glucose will be recorded on day 0; end of week 2 and end of the intervention. Participants in the intervention group will be asked to use an indoor air purifier (Atlanta Healthcare 7-Stage 43-Watt Air Purifier) daily for 4 weeks between the hours of 8 PM and 8 AM. The purifier will be placed in their bedroom or in the room where participants sleep at night. When the participants are outdoors (commuting, working outdoors, running errands, etc.), they will be asked to use a N95 mask (PureMe Reusable N95 Anti-Pollution Mask). It is a reusable mask which can be washed by the participants. Every 2 weeks, the filter of the mask will be replaced, and the filter of the indoor purifier will be washed.

Washout period:

At the end of either control or intervention arm, participants will have a washout period of 2 weeks, after which participants will be crossed over to the other group for the subsequent 4 weeks. For example, after Participant AB is in intervention arm for 4 weeks, he/she will then have a wash out period of 2 weeks in which they will return to their usual state of living. At the end of the washout period, the participant AB will be put in the control arm for 4 weeks.

Control group:

Control arm will be for 4 weeks. Blood pressure, blood glucose and indoor air pollution level will be recorded similarly as in the intervention group on day 0, end of week 2 and week 4. The participant will be provided an air purifier and a N-95 mask (of the same manufacturer), with the filter removed. At the end of two weeks, the health worker will make dummy adjustments to the mask and indoor air purifier, to maintain blinding of the participant.

Study outcomes:

Primary:

- 1. Absolute decrease in systolic blood pressure for people with hypertension using air purifier and facemask
- 2. Absolute decrease in fasting blood glucose for people with diabetes using air purifier and facemask

Data Collection:

All data in the screening questionnaire will be entered by the data entry operator in predesigned database forms in a RedCAP database.

Analysis:

Analysis will be done on an intention to treat basis. Marginal (GEE) models will be used to analyze the data.

Measurements and definitions:

Pollution measurement and recording:

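### The primary contrast, its visit and the role of each period's Day 0 are left open; a within-person Day 0 adjustment and, for diabetes, a small-sample standard error would settle the analysis at little cost

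*Combined protocol and SAP*

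**What the plan says.** Under Study outcomes, the hypertension outcome is "Absolute decrease in systolic blood pressure for people with hypertension using air purifier and facemask". The diabetes outcome has the same form, for fasting glucose. Neither names a reference reading or a time point.

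Under Study Aim 1, Design and Method, "blood pressure and blood glucose levels will be recorded on Day 0, end of week 2 and end of week 4" in each 4-week arm. Between the arms, "there will be a washout period of 2 weeks in which the participants will return to their usual state". Participants serve as their own controls.

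The Analysis section specifies intention to treat and adds that "Marginal (GEE) models will be used to analyze the data". It lists no response variable, visit, period term, covariate, working correlation or type of standard error.

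The sample size section gives "128 participants (calculated with 80% power; alpha level of 0.05; to detect the difference of 2mmHg; assumed SD 8) with hypertension" and "33 participants (calculated with 80% power; alpha level of 0.05; to detect the difference of 10mg/dL; estimated SD 20) with diabetes". The tables beneath label these "128 paired observations" and "33 paired observations". The section does not say what SD 8 and SD 20 are SDs of.

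**The concern.** Several analyses fit this wording: week-4 levels compared between conditions, changes from each period's Day 0 compared between conditions, or either of these averaged over weeks 2 and 4. They have different variances, so the planned 128 and 33 do not give the same power for each. The word decrease invites a change score, while the paired sample size fits either levels or changes.

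Day 0 is collected in both periods and could reduce variance, but only if it enters the model in a suitable form. With 33 participants in the diabetes group, the usual uncorrected GEE standard error is also too small.

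**Working it through.** **Inputs.** From the sample size section: alpha 0.05, power 80%, 2 mmHg with SD 8, 10 mg/dL with SD 20. Sidedness is not stated; two-sided reproduces the figures. Assumed, because the documents do not give it: r, the correlation between the Day 0 and week-4 within-person differences (intervention minus control), with equal variances, over 0, 0.25, 0.5 and 0.75.

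**Step 1: reproduce the plan.** A two-sided paired t-test, with S as the SD of the paired difference, needs n = 127.52 for hypertension and 33.37 for diabetes. Rounded to the nearest whole number, these are 128 and 33. All 18 table cells match in this way, or to within 1 if rounded up. Power is 80.2% at 128 and 79.5% at 33. A one-sided test would need 101 and 27, and two independent groups 252 and 63 per arm. If the SDs were those of a single reading, the required n would be 178/128/78 and 46/34/21 at between-period correlation 0.3/0.5/0.7, so that reading gives the planned sizes (to within 1) only when the correlation happens to be 0.5.

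**Step 2: analyse levels or changes.** Reading A: S is the SD of level differences, so the SD of differences in change is S√(2(1−r)). Reading B: S is the SD of differences in change, so the SD of level differences is S/√(2(1−r)). For example, under A with r = 0, the change SD is 8√2 = 11.31 and power at 128 is 51%.

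**Step 3: adjust for Day 0 within person.** The adjusted SD is the level SD times √(1−r²). The calculation uses n−3 degrees of freedom and inflates the variance by 1 + 1/(n−4) for the extra parameters. Under A with r = 0.5, the adjusted SD is 8√0.75 = 6.93.

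| Power at planned n | r=0 | 0.25 | 0.5 | 0.75 |
|---|---|---|---|---|
| A, hypertension, change score | 51% | 63% | 80% | 98% |
| A, hypertension, adjusted | 80% | 82% | 90% | 99% |
| A, diabetes, change score | 50% | 62% | 80% | 98% |
| A, diabetes, adjusted | 78% | 81% | 88% | 99% |
| B, hypertension, raw level | 98% | 93% | 80% | 51% |
| B, hypertension, adjusted | 98% | 94% | 90% | 85% |

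Under A the raw level has 80.2% (hypertension) and 79.5% (diabetes) at every r. At r = 0 adjustment lowers these to 79.8% and 78.0%, a cost of 0.4 and 1.5 points.

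**Step 4: form of the adjustment.** In a simulated GEE (exchangeable, treatment and period, week-4 rows, n = 128, reading A, r = 0), Day 0 as a single covariate gave power of about 74% and 65–66% at between-period correlation 0.5 and 0.7. Without Day 0, and with Day 0 plus the participant's mean Day 0, it was 81–82%. At r = 0.5 the single covariate gave 89% and 86%, against 81% unadjusted.

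**Step 5: type I error at n = 33.** Simulated under no effect, the uncorrected sandwich z-test rejected in 6.4–7.0% of trials without Day 0 and 7.0–7.5% with the adjusted model. A Kauermann-Carroll standard error with a t reference, or the paired regression with t, gave 4.8–5.2%.

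**Step 6: residual effect at the second Day 0.** Suppose 25% of a 2 mmHg effect (0.5 mmHg) remains at that reading and is gone by week 4. Only the half of participants who had the intervention first are affected, so the mean Day 0 difference is 0.25. The adjusted estimate is 2 + 0.25r, which is 2.06/2.12/2.19 at r = 0.25/0.5/0.75. The raw level gives 2.00 and the change score 2.25.

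**The case against.** The strongest reply is that the design already supplies most of the answer. Own control, paired observations and the aim of comparing the conditions together imply intervention minus control. That stands. What remains open is the visit, levels or changes, and the role of Day 0.

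Four stronger readings are tempting, and the documents do not support them.

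- **The plan leaves Day 0 out of the GEE.** A reader might infer this, but the model's terms are not listed at all. Day 0 is unspecified, not excluded.
- **Adjustment is a sure gain in precision.** The gain depends on r, which the documents do not give. At r = 0 there is none.
- **The trial has about 50% power.** That needs an analysis that does not match the SD and an r at one end of the assumed range. At the other end the same mismatch raises power to 98%.
- **Day 0 must never be a single covariate.** The loss occurs when r is low. At r of about 0.5 or more that form also gains, so the person-mean form is a preference.

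It is also fair to object that the second Day 0 follows treatment, so adjustment relies partly on the 2-week washout. An unadjusted primary analysis with an adjusted sensitivity analysis would be defensible. That stands as a trade-off, and is why both should be reported.

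**Conclusion.** The point holds as a recommended change. The primary contrast is not defined closely enough to identify one analysis, and the power of 128 and 33 depends on that choice: 51% to 98% for hypertension when analysis and SD do not match, over r from 0 to 0.75. Within-person Day 0 adjustment costs at most 0.4 points (hypertension) or 1.5 points (diabetes) against a raw level, and may gain up to about 19 points at r = 0.75 (80% to 99%). These figures assume equal variances, complete pairs and a week-4 contrast. They also assume that the SD is that of a level difference, or of a difference in change where marked. If SD 8 or SD 20 describes something else, such as a single reading, power must be restated, and adjustment cannot be relied on to make up the difference. The type I error of about 6.5–7.5% in the diabetes group applies if the GEE is run with its usual uncorrected standard error, which the plan neither specifies nor rules out.

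**What to change.** 1. Define each primary outcome as the within-person intervention-minus-control difference at a named post-baseline visit, or for the mean of weeks 2 and 4, as the sponsor chooses. State that SD 8 and SD 20 are SDs of that difference. If they are not, restate the power.
2. Fit the GEE with treatment, period, same-period Day 0 and the participant's mean Day 0. If weeks 2 and 4 are separate rows and week 4 is the contrast, add visit and treatment-by-visit terms.
3. For diabetes, use a small-sample-corrected standard error with a t reference, or regress the paired difference on the uncentred Day 0 difference with a period term, using t.
4. Report the same model without Day 0 as a sensitivity analysis. State how participants with only one period are handled under intention to treat; for them, mean Day 0 equals own Day 0.
5. Treat any precision gain as reserve, not as a reason to reduce n.

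The cost is wording in three sections and no new data. The small-sample correction lowers nominal diabetes power (at r = 0 under reading A, from 82–83% with inflated type I error to 77–78%). The adjusted estimate takes in part of any effect still present at the second Day 0. The result is reported as a difference between conditions rather than as a decrease.

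### The GEE analysis has no small-sample method; with uncorrected robust errors and a normal reference, the 33-participant diabetes comparison would be tested at about 6.3-6.7%, not 5%

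*Combined protocol and SAP*

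**What the plan says.** The Analysis section under Study Aim 1 has two sentences: "Analysis will be done on an intention to treat basis" and "Marginal (GEE) models will be used to analyze the data". Neither these nor any other section names a variance estimator, a working correlation, model terms, a reference distribution or a small-sample correction.

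Design and Method describes a "prospective, randomized cross over study in which participants will act as their own control". It also says that "blood pressure and blood glucose levels will be recorded on Day 0, end of week 2 and end of week 4" in each four-week period.

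Sample size and power calculation gives "33 participants (calculated with 80% power; alpha level of 0.05; to detect the difference of 10mg/dL; estimated SD 20) with diabetes", and the matching table cell reads "33 paired observations". The hypertension comparison is sized at 128 participants (difference 2 mmHg, SD 8). Study outcomes lists the fall in fasting glucose in people with diabetes as one of two primary outcomes.

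**The concern.** Because each person supplies both treatment periods, the independent unit for the GEE is the participant, so the diabetes analysis has 33 clusters. Extra readings per person do not increase that number. The ordinary sandwich variance is biased downwards when clusters are few, and a normal reference ignores the uncertainty in the estimated variance. Both errors make the standard error or the critical value too small.

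An analyst who follows the Analysis section literally could therefore test a primary comparison above the stated 0.05 and report intervals that are too narrow. If the choice stays open, it can also be made after the results are seen.

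**Working it through.** **Inputs.** From Sample size and power calculation: n = 33 (diabetes) and 128 (hypertension), alpha 0.05, power 80%, difference 10 mg/dL, SD 20. The plan does not state sidedness. Two-sided is assumed because it reproduces the sample size and one-sided does not (27).

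**1. The plan's own figure.** SD 20 is read as the SD of within-person differences; an unpaired comparison would need 63 per arm.
- Normal formula: (1.960 + 0.842)² × (20/10)² = 31.40.
- Paired t (noncentral t): 33.37, which rounds to the nearest whole number as 33. Power at 33 is 79.5%; 34 are needed to pass 80%.
- Across the two tables, the paired t calculation rounded to nearest matches 18 of 18 cells. The normal formula matches none, whether rounded up or to nearest.

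**2. Level of the uncorrected test.** Take one reading per period, complete data and normal differences dᵢ. The GEE treatment estimate is then the mean difference d̄, and the uncorrected sandwich variance is Σ(dᵢ − d̄)²/n². This equals the usual s²/n multiplied by (n − 1)/n. Rejecting when |z| > 1.96 is therefore the same as rejecting when the paired t statistic exceeds 1.96 × √((n − 1)/n). With a period term, n − 1 becomes n − 2. That version is exact for equal sequences and a close approximation for 33, which cannot split evenly.

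| | Treatment only | With period |
|---|---|---|
| n = 33 | P(\|t₃₂\| > 1.930) = 6.25% | P(\|t₃₁\| > 1.900) = 6.68% |
| n = 128 | 5.31% | 5.41% |

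Simulating the period-adjusted case with sequences of 16 and 17 gives 6.68%. These levels do not depend on the assumed SD or effect.

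**3. Interval width at n = 33, SD 20.** SD/√n = 20/√33 = 3.48.
- Treatment only: 1.96 × √(32/33) × 3.48 = 6.72, against 7.09 mg/dL for the t interval. Coverage is 93.7%.
- With period: 1.96 × √(31/33) × 3.48 = 6.61, against 7.10 mg/dL. Coverage is 93.3%.

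**4. Do the repeated readings change this?** Simulated null trials at n = 33 used normal data. The first two rows use an exchangeable GEE with all correlations 0.5 (assumed); the last uses working independence.

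| Model | Uncorrected sandwich, z | Kauermann-Carroll, t |
|---|---|---|
| Treatment only, one / two readings per period | 6.3% / 6.3% | 5.0% / 5.0% |
| With period, one / two readings | 6.7% / 6.7% | 5.0% / 5.0% |
| Weeks 2 and 4, Day 0 covariate, period | 6.6% | 4.8% (31 df) |

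At n = 128 the uncorrected z test gives 5.3-5.6% across these forms.

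**5. Are model-based errors a way out?** Not reliably. With two readings per period, a period term and a z reference, they give 5.2% if all correlations are 0.5. With 0.5 across periods, they give 8.6% if the within-period correlation is 0.6 and 12.6% if it is 0.7. All of these correlations are assumed.

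**6. Is the assumed setting realistic?** The statsmodels GEE routine at default settings (exchangeable, 33 clusters) rejected in 7.25% of 2,000 null trials, and in 7.1% of 1,500 in a separate run. Simulation error is about 0.6 percentage points in each. Both agree with 6.68% and lie above 5%.

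**The case against.** The strongest reply is that the plan never says it will use an uncorrected sandwich with a normal reference. Other choices compatible with its wording give other levels at n = 33:
- degrees-of-freedom-corrected variance with z: 5.9%;
- uncorrected sandwich with t: 5.3% (treatment only) or 5.7% (with period);
- Mancl-DeRouen with t: 4.4-4.7%.

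This stands. The result is conditional and does not predict what this trial will do.

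It is also fair that a planning formula does not bind the analysis. The match to a paired t calculation shows how the sample size was derived. It supports a t-based analysis but does not make the Analysis section contradictory.

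The 6.3-6.7% range is not a firm bound either. Sealed envelopes are specified without blocking, and a 13/20 split gives about 6.9-7.0%. With 28 analysed (an assumed 15% loss) the range is 6.5-7.0%; with 50 it would be 5.8-6.1%.

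Finally, the variance estimator is only one gap in a two-sentence analysis section that also omits model terms and visits. That is true, but the excess appears in every model form tried, so it need not wait for those other choices.

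**Conclusion.** The concern holds, as a minor one. The named method, run with settings that ordinary software supplies by default, tests the diabetes comparison 1.3-1.7 percentage points above the stated level and gives half-widths 0.4-0.5 mg/dL too short at SD 20. The point estimate is unaffected and hypertension barely changes. The figures assume normal within-person differences, complete data, near-equal sequences and 33 participants analysed. The choice of uncorrected sandwich with a normal reference is an assumption about how the silence would be filled.

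**What to change.** Add to the Analysis section under Study Aim 1:

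> GEE inference will use a small-sample bias-corrected sandwich covariance (Kauermann-Carroll) with a t reference distribution; for the model with treatment and period, the degrees of freedom are the number of participants minus 2 (31 for 33 participants).

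If period is left out, use participants minus 1 (32). The convention matters little: the period-adjusted t test on 30, 31 or 32 degrees of freedom has level 4.97%, 5.00% or 5.03%.

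Another pre-specified small-sample method would also serve, such as Mancl-DeRouen, or a paired or mixed-model analysis with small-sample degrees of freedom. If Mancl-DeRouen is chosen, state the reference distribution too: for the models with one or two readings per period it gives 5.2-5.5% with z and 4.4-4.7% with t. The same sentence can cover hypertension.

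The cost is one sentence and a software option. The diabetes half-width grows from 6.72 to 7.09 mg/dL (treatment only) or from 6.61 to 7.10 (with period), about 5-7%. Power at 10 mg/dL is 79.5%, the same as the paired t calculation at 33. The uncorrected test shows 82.4-83.2% only because its level exceeds 5%.

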Given that there is no pollution monitoring unit in or near Dalkhola, we plan to directly record the pollution level in Dalkhola. We will be using Airveda Outdoor PM 2.5, PM 10 air quality monitor to record ambient air pollution levels. Ambient (Outdoor) air pollution level recording will include: Average PM 2.5 level, Average PM 10 level, Peak PM 2.5 level, Trough PM 2.5 level, AQI (Air quality index), Average temperature and Average humidity. Indoor air pollution level will be recorded using Airveda Smart Air Quality Monitor. Because the personal air pollution level depends on the indoor/outdoor ratio, which is beyond the scope of this study, we will assume that it is the same for all participants and thus, will record the indoor air pollution level at the site where participants sleep at night.

Blood pressure measurement:

The blood pressure will be measured using an electronic BP machine (Omron HEM- 8711). The average of the last two of three left-arm blood pressure measurements after a minimum of 5 minutes of rest with the participants seated with feet on the floor and arm supported at heart level will be used.

Blood glucose measurement:

The capillary blood glucose levels will be measured using handheld blood glucose meters (Accucheck Performa). The participant is educated on the importance of fasting at the initial visit and fasting status will also be confirmed prior to a measurement. The finger prick will be made (sterile lancet after swabbing with spirit swab) on the left ring finger and capillary blood glucose will be measured and recorded.

Study Aim 2:

To understand the knowledge, attitude and perception of people with hypertension and/or diabetes regarding air and noise pollution and its health effects.

Design and Method:

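### Fasting glucose, a primary outcome sized at 33 pairs, appears to rest on one handheld-meter reading per visit; duplicate strips would cheaply recover some precision.

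*Combined protocol and SAP*

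**What the plan says.** Under Study Aim 1, Study outcomes, the second of two primary outcomes is "Absolute decrease in fasting blood glucose for people with diabetes using air purifier and facemask".

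Under Blood glucose measurement, "The capillary blood glucose levels will be measured using handheld blood glucose meters". Fasting status is confirmed, the finger is pricked, and the value is recorded: "capillary blood glucose will be measured and recorded". The section does not mention a second strip, an averaging rule, a quality check of the meter, or use of the same meter for a participant across visits. It does not say in terms that only one reading is taken; that is inferred from the singular wording.

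Under Blood pressure measurement, directly before it, the recorded value is "The average of the last two of three left-arm blood pressure measurements".

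Under Sample size and power calculation, the diabetes group is "33 participants (calculated with 80% power; alpha level of 0.05; to detect the difference of 10mg/dL; estimated SD 20"), and the accompanying table labels the 33 as paired observations. Glucose is recorded on day 0 and at weeks 2 and 4 of each 4-week period, so there are six visits per person. The Analysis paragraph names GEE models but does not say which visits form the primary contrast.

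**The concern.** Both primary outcomes vary from reading to reading. The plan averages this out within a visit for blood pressure, in the larger group (128 participants), and not for glucose, in the smaller one (33). Any random strip error in a single reading passes whole into that visit's value. A crossover difference between two visits then carries it twice.

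What is at stake is the width of the confidence interval for the second primary outcome. The glucose calculation has no slack and no stated allowance for dropout, so a source of variance that can be reduced without more participants or visits deserves attention.

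**Working it through.** **Inputs from the documents.** n = 33 pairs, difference 10 mg/dL, SD 20 mg/dL, "alpha level of 0.05", 80% power, entry range 126-180 mg/dL. Sidedness is not stated; two-sided is inferred because it reproduces the plan's figure.

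**Assumption.** The documents give no meter precision. I take a random error SD per reading of m = 3, 4.5 or 7.5 mg/dL (2%, 3% or 5% of 150 mg/dL, near the middle of the entry range).

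**Step 1: the plan's figure.**
- The normal formula gives n = ((1.960 + 0.842) × 20/10)² = 31.4, so 32. The noncentral t gives 34. The stated 33 lies between them.
- Power at 33 pairs is 79.5% by paired t (81.9% by the normal approximation).
- A one-sided paired t would need 27, and two independent groups 63 per arm. SD 20 is therefore being used as the SD of within-person differences.
- The same two-sided paired t returns exactly 128 for blood pressure.

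**Step 2: week-4 versus week-4 contrast, SD 20 already including single-reading error.** Each difference contains 2m² of meter variance out of 20² = 400. Duplicates remove m², so the new SD is √(400 − m²).

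| m (mg/dL) | Meter share, 2m²/400 | SD with duplicates | Power at 33 pairs |
|---|---|---|---|
| 3 | 18/400 = 4.5% | √391 = 19.8 | 80.4% |
| 4.5 | 40.5/400 = 10.1% | √379.75 = 19.5 | 81.6% |
| 7.5 | 112.5/400 = 28.1% | √343.75 = 18.5 | 85.2% |

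Against 79.5%, the gain is about 1 to 6 percentage points.

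**Step 3: weeks 2 and 4 averaged in each period.** Meter variance in the contrast is now 2m²/2 = m², and duplicates remove m²/2. If SD 20 is the SD of this averaged contrast, the new SD is √(400 − m²/2) = √395.5 = 19.9, √389.9 = 19.7 or √371.9 = 19.3. Power is 80.0%, 80.5% or 82.3%, a gain of about 0.5 to 3 points. Treating SD 20 instead as the single-visit SD, with an assumed correlation of 0.5 to 1.0 between the week-2 and week-4 differences apart from meter error, gives gains in the same range.

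**Step 4: SD 20 excluding meter error.** The source of SD 20 is not stated. For the week-4 contrast, single readings then give SD √(400 + 2m²) and power 77.8%, 75.6% or 69.2%. Duplicates give √(400 + m²) and power 78.7%, 77.6% or 74.2%. The gain is again about 1 to 5 points.

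**Step 5: how to use a third strip.** I simulated a rule that adds a third strip when the first two differ by more than 15 mg/dL (an illustrative threshold), with normal errors. At m = 4.5 and 7.5, averaging the two closest of three leaves 0.52 and 0.58 of the single-reading meter variance. Averaging all three leaves 0.50 and 0.47. Third strips are triggered at about 2% and 16% of visits. Choosing the two closest is worse than plain duplicates (0.50).

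**The case against.** The strongest reply is that nothing here is an error. If SD 20 came from single meter readings, the 33 pairs already pay for strip noise, and duplicates only lift power above what was planned. Averaging blood pressure does not oblige the sponsor to average glucose. Participants and the measuring health worker are blinded, so random strip error should be alike in both periods and costs precision only. All of this stands, and it is why the point is an improvement and not a defect.

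Three stronger inferences are tempting, and the documents do not support them.

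- **That meter error enters the result undiluted.** This holds within a visit only. There are six visits per person, and a GEE model using several of them averages part of the error. A contrast based on change from day 0 would instead bring in more readings; the plan does not settle which applies.
- **That strip error rivals the 10 mg/dL target.** That compares one person's reading with a group mean. Over 33 pairs with single week-4 readings, meter error alone contributes √(2/33) × m to the standard error of the mean difference: 0.7 to 1.8 mg/dL for m = 3 to 7.5. One strip that is wrong by 30 mg/dL moves the mean by 30/33 = 0.9 mg/dL.
- **That the gain could reach 11 points (79.5% to 90.5%).** This needs a 7% error (10.5 mg/dL), at which strip noise would be 2 × 10.5²/400 = 55% of the paired variance. Nothing in the documents supports so large a share.

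It is also fair to say that two strips from one prick share any fault in the blood drop, and that repeats on one meter do not reveal a constant offset. These limit the gain but do not remove it.

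**Conclusion.** The point holds as a cheap improvement of low to moderate severity. As written, the plan provides one handheld reading per visit for a primary outcome with 79.5% power, so random strip error is not averaged within a visit. Bias is not shown.

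With an assumed error SD of 3 to 7.5 mg/dL contained in SD 20, duplicates raise power at 33 pairs to about 80.4% to 85.2% for a week-4 contrast. If weeks 2 and 4 are averaged, the gain is about 0.5 to 3 points. The size depends on meter precision, the source of SD 20 and the choice of visits, none of which the documents give. The direction does not: with independent strip errors, a mean of two readings is at least as precise as one.

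**What to change.** In the Blood glucose measurement section, specify two strip readings from the same finger prick at every diabetes visit, with the same meter for a participant throughout both periods. Record both values and analyse their mean. If a third strip is to be taken when the two differ by more than a preset amount, fix that amount in advance and use the mean of all three, not of the two closest. It would also help to state where SD 20 comes from and which visits form the primary contrast, since these determine how much is gained.

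Cost: 33 participants × 6 visits = 198 extra strips, any third strips, and about a minute per visit. No extra pricks, visits, staff or participants are needed. Day-to-day biological variation and any error shared by the blood drop are not reduced. If duplicates are already intended, one sentence saying so closes the point.
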